We will limit sources of and account for potential contamination in our data pipeline, such as in reagents and kits (60,61) and in processing MiSeq-generated sequences (62,63). We will handle contamination issues by: 1) eliminating OTUs that are substantially increased when total 16S is low, 2) randomize samples to different extraction kits and re-run with a different lot-numbered kit to confirm findings, 3) do phenol-chloroform extractions instead of relying exclusively on kits, 4) maintain consistency in kits and lots for each analysis, and 5) cycle bar codes between runs.

We will use FASTX-Toolkit for quality trimming of Illumina files. The QIIME pipeline is used for primer trimming, chimera checking and sequence alignment, taxonomic classification and calculation of α and β diversity indices, and generation of rarefaction curves. We construct an abundance matrix of reference OTUs and phylogenetic trees derived from the GreenGenes reference set (64). We will employ a suite of multivariate statistical tools to compare amplicon data between and within sample types by canonical correlation analysis, regression profiling, and visualization (e.g. non-metric multi-dimensional scaling [NMDS], Principal Coordinates of Analysis, and Principal Components Analysis). We will also look at the species diversity of each sample and observe if there is any variation between the cohorts. In addition, we will use nonparametric statistics (ANOSIM, ADONIS, ANOVAR, PERMANOVA, etc.) to determine the statistical significance of participant factors. Significance of differences in relative percentage and diversity indices between groups will be calculated using Student's t-test. The Pearson correlation coefficient will be used to assess correlations among continuous variables.

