Microbial bioinformatics. We will employ a suite of multivariate statistical techniques, network modeling and machine learning approaches to characterize the composition and structure of the microbial community between and within the normal subjects and asthma experimental arms, and determine microbial biomarkers that correlate with ACT score, albuterol use, changes in FEV1, and markers of airway inflammation. All amplicon sequencing data will be quality filtered and de-multiplexed and then subjected to de novo operational taxonomic unit (OTU) picking, and sub-OTU characterization using DeBlur (<https://github.com/biocore/deblur>.) Microbial diversity will be summarized using Chao1 estimator and Shannon index, and association with clinical and immune variables will be tested by regression analysis and generalized linear modeling. UniFrac distances (between-sample beta diversity) will be used to visualize and test the overall microbiota structure difference between study arms using multivariate methods such as principal coordinate analysis (PCoA) and permutational multivariate analysis of variance (PERMANOVA). DESeq2, which allows correction for multiple testing, will be used to perform differential abundance analysis to identify clinically relevant taxa (65). Based on these results, logit models will be generated using dichotomized clinical and immune variables as outcomes, and the microbiome data as independent variables. Variable selection methods will be integrated to avoid over-fitting. Since we expect that the number of genera will be approximately equal to 300, a dimension reduction will be performed so that efficient statistical inference can be conducted, using either the LASSO (66) or thresholding (67) methods within the context of high-dimensional inference for generalized linear mixed effects models. Classification performance will be evaluated using ROC curve and the 0.632+ bootstrap method (68). The machine learning approach, Random Forest, will also be applied to determine whether the microbiome is predictive of clinical outcomes (69). We will also examine whether there are natural grouping patterns in the microbial community data and, if so, how these grouping patterns relate to asthma phenotypes. To do this, we will compute Bray-Curtis dissimilarity measures between subjects and perform hierarchical cluster analysis and nonmetric multidimensional scaling to visualize if the groupings determined by the hierarchical clustering algorithm relate to asthma phenotypes. We will also fit multivariate analysis of variance (70) and ordination models for the relative abundance of the microbiome response against the treatment and time effects using the R package vegan (71).

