
We will analyze changes from the pre- to post-azithromycin treatment, and between azithromycin and placebo subjects, in 1) abundance of key microbial genera (e.g., *Pseudomonas*, on which our first power calculations are generated, as well as *Streptococcus* and *Hemophilus*), 2) change in alpha-diversity, richness and evenness indices, 3) principal coordinate analysis (PCoA) and non-metric multi-dimensional scaling (NMDS) of beta-diversity indices, and 4) com-

parisons of key changes to clinical parameters of most compelling interest: ACT score, methacholine responsiveness, FEV1, markers of airway inflammation such as BAL eosinophils and neutrophils, BAL concentrations (measured by multiplex assay) of Th2 related cytokines such as IL-5 and IL-13, IL-17 related cytokines such as IL-17a, and TGF- β 1. The measurement of Th17-related cytokines is particularly important as we anticipate that 70% of our subjects will have a blood eosinophil count < 300 per μ l or BAL eosinophil proportion < 3%, and azithromycin may be more effective in patients with eosinophil-low asthma (20).

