Poisson modeling of relative abundance. To test for differences in relative abundance of key microbial genera between the placebo and azithromycin groups at each time point and over time, we will fit a Poisson regression model with treatment and time as fixed effects with offset (for the total abundance) and with subjects as random effects for the microbial genera of interest (72). Since missing data may be present in the data set, we will create a multiple imputation simulation function in R for generalized linear mixed effects models to improve efficiency of inference and to assess sensitivity of the model over multiple imputations using the R package mice. We will use the specific Poisson regression model to impute the missing values to obtain further efficiency in the data analysis. Based on the Poisson regression model fit, we will make inference for alpha, beta, and gamma diversity measures. These measures will be calculated using either Shannon entropy or the inverse Simpson index (in this context, the habitats of the microbiome genera are the samples collected on the treatment groups over time). Power and sample size calculations for the U01 RCT will be performed based on the fitted Poisson and multivariate regression models. If a test statistic is not significant in the pilot study, we will use mathematical statistical properties of the test statistics (such as the likelihood-ratio, the Wald test, or the score test statistics) under the alternative hypothesis which will allow us to generate power as functions of the sample size. We will create an R package in which we implement all statistical methods in the data analysis work-flow and create R markdown files with fully reproducible data analyses and description of statistical methods. In this way, the data analysis can be easily replicated. If new statistical methods are developed as a result of this complex multi-faceted data analysis, we will write a methodological paper for submission to a statistical journal.

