Power calculations. Power calculations are difficult given the paucity of data about changes in the airway microbiome. This is explicitly an exploratory protocol to ascertain whether, in the short term, treatment of azithromycin in a small cohort of asthmatics changes the lower airway microbiome. We can generate potential power calculations based on the difference in (for example) relative abundance of pathogens in lower airway samples. For this protocol, a key goal is to obtain a good estimate of just how much the microbiome changes in response to azithromycin: if substantial, this trial will aid greatly our ability to make power calculations for larger trials. If changes are small, we will have a clear answer at a modest cost. For example, based on our preliminary published data (25), *Pseudomonas* abundance among asthma patients using ICS was $10.4 \pm 1.8\%$. Assuming 20 evaluable patients on azithromycin in a before and after analysis, we will have 80% power (two-sided $\alpha=0.05$) to detect a change in abundance of $\Delta=0.9$ to $\Delta=1.2$ if the within-patient correlation between pre- and post-treatment abundance is $\rho=0.7$ or $\rho=0.5$. The half-width of the 95% confidence interval for the change in abundance will be 0.7 to 0.84 if $\rho=0.7$ or $\rho=0.5$.

BIBLIOGRAPHY AND REFERENCES CITED

1. (EPR3) EPR. Guidelines for the Diagnosis and Management of Asthma. Bethesda: National Heart Lung and Blood Institute; 2007.
4. Braman SS. The global burden of asthma. *Chest.* 2006; 130(1 Suppl):4S-12S.

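### The Poisson mixed model for genus abundance has no term for visit-to-visit variation, so its tests of change over time reject far too often

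*Combined protocol and SAP*

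**What the plan says.** All references are to the combined protocol and SAP, Statistical analysis section.

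- *Poisson modeling of relative abundance*: to compare the arms on key genera, at individual visits and across visits, the analysts will "fit a Poisson regression model with treatment and time as fixed effects with offset (for the total abundance) and with subjects as random effects". No dispersion parameter, visit-level random effect, negative-binomial form or robust standard error is named. The opening part of the section, which assigns Poisson mixed models to count outcomes in general, names none either.
- The same paragraph gives the fit further uses. For missing data: "We will use the specific Poisson regression model to impute the missing values". For the next trial: "Power and sample size calculations for the U01 RCT will be performed based on the fitted Poisson and multivariate regression models". Inference on alpha, beta and gamma diversity also rests on it.
- *Microbial bioinformatics* sets the comparisons of interest: "We will analyze changes from the pre- to post-azithromycin treatment, and between azithromycin and placebo subjects".
- *Power calculations*: *Pseudomonas* "abundance among asthma patients using ICS was" 10.4 ± 1.8%, with an assumed pre/post correlation of 0.7 or 0.5. "The half-width of the 95% confidence interval for the change in abundance will be 0.7 to 0.84" at those two correlations, for 20 evaluable patients.

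**The concern.** Given the subject effect, the model allows a patient's genus count to vary between visits only by Poisson sampling of reads. Real change in the airway community from visit to visit, unrelated to treatment, has nowhere to go. It is read as signal, and the standard errors of within-patient contrasts (time, and treatment by time) come out too small.

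Estimating how far the microbiome moves under azithromycin is a stated key goal of this pilot, and the answer is meant to inform the RCT. A model that understates the variance of change could report genus shifts that the plan's t-tests would not support. Imputations drawn from it would show too little visit-level spread. It would also give optimistic input to any sample size built on its change contrast.

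**Working it through.** **Inputs**

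- Mean 10.4%, spread 1.8 points, ρ = 0.7 or 0.5, n = 20, two-sided 5%, 80% power: *Power calculations*. The 1.8 is not labelled there; step 1 shows that it is used as an SD.
- 20 per arm: 40 asthma subjects randomized 1:1 (*Study Design*).
- Reads per sample, N: **an assumption**. *Initial microbiome analysis* mentions 10,000 reads only as a coverage benchmark. Range examined: 1,000 to 50,000.

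**1. Reproduce the plan's figures.** SD of change = 1.8 × √(2(1 − ρ)) = 1.394 (ρ = 0.7) or 1.800 (ρ = 0.5). Half-width = 2.093 × SD/√20 = 0.65 or 0.84. The change detectable by a paired t-test on 19 df is 0.92 or 1.19. These match the stated 0.7 to 0.84 and 0.9 to 1.2 after rounding.

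**2. Visit-to-visit variance in those figures.** 1.8² × (1 − ρ) = 0.972 or 1.62, an SD of 0.99 or 1.27 points.

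**3. Variance the model allows.** In squared percentage points, 10.4 × 100/N = 0.104 at 10,000 reads, an SD of 0.32 points. The two agree only at N = 1,040/0.972 = 1,070 or 1,040/1.62 = 642 reads.

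**4. Size of a nominal 5% test of change.** With R = (step 2)/(step 3), type I error = 2 × [1 − Φ(1.96/√R)].

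| Reads | R (ρ 0.7 / 0.5) | Type I error (ρ 0.7 / 0.5) |
|---|---|---|
| 1,000 | 0.93 / 1.56 | 0.043 / 0.116 |
| 2,000 | 1.87 / 3.12 | 0.152 / 0.267 |
| 5,000 | 4.67 / 7.79 | 0.365 / 0.482 |
| 10,000 | 9.35 / 15.58 | 0.521 / 0.619 |
| 20,000 | 18.69 / 31.15 | 0.650 / 0.725 |
| 50,000 | 46.73 / 77.88 | 0.774 / 0.824 |

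Standard errors of change are too small by √R: 3.1 to 3.9 at 10,000 reads and 1.4 to 1.8 at 2,000. The table takes 1.8 to include read noise already. If it does not, R rises by 1 and the error is 0.54 / 0.63 at 10,000 reads and 0.16 / 0.22 at 1,000.

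**5. Fitted-model simulation.** Random-intercept Poisson GLMM (Laplace), 20 per arm, 10,000 reads, no true effect, 1,500 runs per setting:

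| Test | Two visits (ρ 0.7 / 0.5) | Three visits (ρ 0.7 / 0.5) |
|---|---|---|
| Treatment by time | 0.545 / 0.642 | 0.538 / 0.639 |
| Time | 0.535 / 0.621 | similar |
| Arm difference at one visit | 0.093 / 0.100 | 0.098 to 0.139 |
| Treatment main effect | 0.080 / 0.061 | 0.067 / 0.075 |

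In 20,000 simulated trials under the same assumptions, a t-test on within-patient change in log abundance rejected 5.3% / 4.9% between arms.

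**6. Precision for 20 patients, before and after.** The Poisson model gives 1.96 × √(2 × 0.104/20) = 0.20 points at 10,000 reads and 1.96 × √(2 × 0.520/20) = 0.45 at 2,000, against 0.65 or 0.84 in step 1.

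**7. Conditional sizing.** Suppose the RCT were sized from this model's change contrast with its model-based variance, for a 1.2-point difference. Then n per arm = 2 × 7.849 × 2 × variance/1.2². The plan's variance gives 21.2 or 35.3 (22 or 36). The Poisson variance gives 2.27 (3) at 10,000 reads and 11.3 (12) at 2,000. On rounded n the shortfall is 7 to 12 fold at 10,000 reads and 2 to 3 fold at 2,000.

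**8. Does the remedy work?** A negative-binomial mixed model brought the treatment-by-time rejection rate to 2–4%. A log-scale model with an added visit-level variance (REML, 800 runs) gave 6.5% / 5.4%. The Poisson model with an observation-level effect was not itself fitted.

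**The case against.** The strongest reply is about scope. The protocol calls itself exploratory, and no listed outcome depends on the Poisson test alone. *Initial microbiome analysis* says "Significance of differences in relative percentage and diversity indices between groups will be calculated using" Student's t-test, and *Microbial bioinformatics* says DESeq2 "will be used to perform differential abundance analysis to identify clinically relevant taxa". Both allow for the extra variation, and the t-tests on change planned for clinical parameters may also cover the top-10-genera secondary outcome. That is true and limits the harm. But neither replaces the Poisson model for its over-time test, the imputation, the diversity inference or the Poisson-based part of the RCT sizing.

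Second, the listed fixed effects contain no treatment-by-time term, and the treatment main effect, the only between-arm term actually written, is near nominal. This also stands for the model as literally listed. However, comparing arms across visits needs the interaction, and the time effect that is listed is inflated to the same degree.

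Third, the size rests on an assumed read depth, assumed correlations and one genus. The cited source of the 1.8 concerns, by its title, bronchial and lavage samples rather than induced sputum. The figures are therefore illustrative. Near 1,000 reads the inflation could be slight or absent if 1.8 already includes read noise; at greater depth it grows.

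Fourth, the plan never attributes its stated half-width to the Poisson model, and it also names multivariate models for sizing, with no variance method given. So step 6 compares two analyses in one plan that assume different variances, and step 7 is strictly conditional.

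**Conclusion.** The concern holds: the model is wrong as written for within-patient contrasts. On the plan's *Pseudomonas* figures, with 1.8 as an SD and 10,000 reads assumed, nominal 5% tests of time or treatment by time reject a true null in roughly 50–60% of trials. From 2,000 to 50,000 reads the range is 15% to 82%. A single-visit arm comparison is mildly inflated (9–14%) and the treatment main effect close to nominal (6–8%). The documents give no variance for other genera, so the size there is unknown. ACT is unaffected. This should be fixed before analysis because it bears on what the pilot is meant to estimate, but it does not threaten the primary outcome.

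**What to change.** In *Poisson modeling of relative abundance*, replace the model with a negative-binomial mixed model, or add a subject-by-visit (observation-level) random effect to the Poisson model. Keep the log-total offset and the subject random intercept. Write the treatment-by-visit term explicitly, so that the fitted test answers the stated question. Report the estimated dispersion for each genus. Use this fit, not the plain Poisson fit, for the imputation, the diversity inference and the Poisson-based part of the RCT sample-size work. State the intended or minimum read depth as well, since the size of the problem depends on it.

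The cost is SAP wording and a modest amount of programming in the model call, the imputation function and the power code. No new data are needed. Intervals for change will be wider, as the plan's own variance figures require.

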This pilot protocol examines the change in the airway microbiome after azithromycin over an 8 week period. 40 subjects with poorly controlled asthma and 10 control subjects with no known lung disease will undergo clinical data collection including ACT score, lung function, exhaled nitric oxide (FeNO), methacholine challenge, and induced sputum and blood collection. Participants with asthma then are randomized 1:1 to receive azithromycin, 250 mg, or placebo, daily for 8 weeks. Clinical parameters including ACT, oral wash, adherence, side-effect profile, spirometry, and biological specimens (sputum, blood, FeNO) are collected again at 4 and 8 weeks. Control subjects undergo the same measurements, but do not receive any intervention.

Schedule of Events

	Asthma (A) or Control (C)	Visit 1/Week 0 (Screening) (+/- 3 days)	Visit 2/Week 4 (+/- 3 days)	Week 6 (+/- 3 days)	Visit 3/Week 8 (+/- 3 days)	Week 10 (+/- 3 days)	Visit 4/Week 12 (+/- 3 days)	Week 14 (+/- 3 days)
Informed Consent	A,C	X						
Site Visit	A,C	X	X		X		X	
Phone Call	A			X		X		X
Confirmation of Eligibility	A,C	X	X					
Randomization	A		X					
Drug Dispensation	A	X ^{1,2}	X ^{1,2,3}		X ^{1,2,3}		X ^{1,2}	
Demographics	A,C	X						
Medical History Review	A,C	X						
Asthma History	A	X						
Smoking History	A,C	X						
Concomitant Medication Review	A,C	X	X		X		X	
Physical Exam/Vital Signs	A,C	X	X		X		X	
Asthma Control Test	A	X						
Demographics Questionnaire	A,C	X						
Family History Questionnaire	A,C	X						
Work Exposures Questionnaire	A,C	X						
Home Exposures Questionnaire	A,C	X						
Physical Activity Questionnaire	A,C	X						
Secondhand Smoke Exposure Questionnaire	A,C	X						
Peak Flow Meter Readings ⁵	A	X	X	X	X	X	X	X
Electronic Diary ⁴	A	X	X	X	X	X	X	X
ECG	A,C	X	X		X		X	
Spirometry with Reversibility ⁶	A,C	X	X		X		X	
Exhaled NO	A,C	X	X		X		X	
Urine Pregnancy Test ⁷	A,C	X						
Methacholine Challenge ⁸	A,C	X	X		X		X	
Sputum Induction	A,C	X	X		X		X	
Oral Wash	A,C	X	X		X		X	
Complete Blood Count with Platelet Count and Differential Blood Sample	A,C	X			X			
Serum IgE Blood Sample	A,C	X						
RAST Blood Analysis	A,C	X						
Research Blood Samples	A,C	X			X			
Adverse Events Review	A,C		X	X	X	X	X	X
Compliance/Adherence to Diary and Study Drugs	A	X	X	X	X	X	X	X

1. Dispensation of albuterol to asthmatic subjects (if required at Visit 2 and Visit 3)
2. Dispensation of ICS/LABA to asthmatic subjects
3. Dispensation of azithromycin/placebo to asthmatic subjects

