Rescue therapy. This will be done using a standard preparation of albuterol, 90 mcg per inhalation, per the device ProAir or equivalent metered dose inhaler. This device is familiar to most asthmatic subjects. Subjects use this medication when required for relief of acute asthma symptoms. Subjects will keep a diary card of the use of albuterol and provide this card to research staff at each visit.

Initial, thorough training in the use of each device is done during visit #1 by research staff using the Teach To Goal method implemented by the Asthma and COPD research team at the University of Chicago (63-65). Adherence to and proper technique in the use of each medication will be assessed at each visit, and will be recorded on forms by research staff. Subjects have a 24/7 access to one of the study physicians or other member of the research team for any problems associated with the use of these medications.

Subjects are instructed not to use other asthma medications during the study without informing research staff. The research lead physicians ([name], [name]) or other member of the research team will contact primary care providers when necessary to ensure appropriate asthma care throughout the study. Subjects return to their prescribed asthma medication use at the end of the trial.

Study Drug

Azithromycin. We have received an exemption from the U.S. Food and Drug Administration (FDA) for the use of azithromycin in this protocol. The dose, 250 mg daily for 8 weeks, is a dose and regimen used in other lung diseases such as bronchiectasis, COPD, and cystic fibrosis (33-40).

Participants with asthma who complete the four week run-in phase (visit 1 to visit 2) will enroll at visit 2 into the study drug phase. They will receive the study drug, azithromycin (250 mg once a day for 8 weeks) or blinded placebo through the end of visit 4. They will be provided with a study drug diary. When they return at Visit 4 the study staff will collect the study drug bottle and count drug remaining. At the time of the telephone review (visit 5) subjects with asthma will be asked about any side-effects from azithromycin/placebo use.

Subjects are cautioned about potential side-effects of the drug and reminded about how to contact a study physician or other member of the research team.

Payment

Subjects will receive \$100 at the end of each visit for a total of \$400. This will come in a form of a check which will be mailed to their home.

Risks

Azithromycin

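### The genus-level Poisson model names no treatment-by-time term, so as worded it cannot test arms by visit; with arm coding over all four sputum visits it keeps only about half the drug effect

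*Combined protocol and SAP*

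**What the plan says.** Under Statistical analysis, the paragraph on Poisson modeling of relative abundance aims to test genus differences "between the placebo and azithromycin groups at each time point and over time". To do so, the sponsor will "fit a Poisson regression model with treatment and time as fixed effects with offset (for the total abundance) and with subjects as random effects". It names no treatment-by-time interaction, baseline adjustment or restriction to on-drug visits. The same paragraph uses this model for diversity inference, for imputing missing values and, with the multivariate models, for power and sample size of the later RCT.

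The Schedule of Events places "Sputum Induction" at Visits 1 to 4 (weeks 0, 4, 8 and 12) and randomization at Visit 2. The Study Drug section says that participants with asthma "who complete the four week run-in phase (visit 1 to visit 2) will enroll at visit 2 into the study drug phase", and that they take azithromycin or "blinded placebo through the end of visit 4". On these texts, Visits 1 and 2 are pre-drug, and Visits 3 and 4 are on drug.

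The Study Design prose differs: after one baseline and randomization, measurements "are collected again at 4 and 8 weeks". That implies one pre-drug visit.

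The Microbial bioinformatics paragraph also plans "ordination models for the relative abundance of the microbiome response against the treatment and time effects using the R package vegan", without a formula.

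**The concern.** A model with a treatment effect and a time effect, and no product of the two, forces the arm difference to be the same at every visit. It therefore cannot deliver the visit-by-visit comparison that it is meant to provide.

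Randomization makes the expected arm difference zero before the first dose. If treatment is coded as arm, the single coefficient mixes those zeros with the on-drug difference, plus any chance imbalance at baseline. It is not the drug effect.

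This matters because estimating the microbiome response for RCT sizing is objective (b) of the pilot. A halved effect with unchanged variance would inflate an RCT sample size by (1/0.5)² = 4. The Power calculations paragraph also says that small changes would be taken as a clear answer, and a diluted estimate could be misread that way.

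**Working it through.** **Inputs.** From Power calculations: SD 1.8 percentage points, within-patient correlation ρ = 0.7 or 0.5, effect Δ = 0.9 or 1.2, two-sided α = 0.05. From Study Design: 40 subjects with asthma allocated 1:1, so 20 per arm. Assumed here: compound symmetry over visits, the same effect at Visits 3 and 4, no missing samples. Power is from the noncentral t with 38 df unless stated.

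**1. The plan's own figure** (one arm, before–after, n = 20, 19 df). SD of change = 1.8√(2(1−ρ)) = 1.394 (ρ = 0.7) or 1.800 (ρ = 0.5). Dividing by √20 gives SE 0.312 or 0.402.
- Detectable change at 80% power: 0.92 or 1.19 (plan: 0.9 and 1.2).
- 95% half-width: 0.65 or 0.84 (plan: 0.7 and 0.84).

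These agree after rounding. As a one-arm calculation, it neither supports nor contradicts the Poisson model; it only supplies the inputs.

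**2. How much of the effect the arm term keeps.**
- Equal weights, two pre-drug and two on-drug visits: (0 + 0 + Δ + Δ)/4 = Δ/2, so 50%.
- Count weights, rate ratio RR: log((2 + 2RR)/4)/log(RR) = 42%, 46% and 49% for assumed RR of 0.5, 0.7 and 0.9. Simulated Poisson mixed models kept 42% (RR 0.5) and 44% (RR 0.7).
- One pre-drug visit: 2/3 = 67% with equal weights; log((1 + 2RR)/3)/log(RR) = 58%, 63% and 65% with count weights.

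**3. Power of the additive arm term** (linear approximation). With four visits, a subject mean has variance 3.24(1 + 3ρ)/4 = 2.511 or 2.025. SE of the arm difference = √(2 × variance/20).

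| Visits fitted | ρ, Δ | Expected coefficient | SE | Power |
|---|---|---|---|---|
| 2 pre, 2 on | 0.7, 0.9 | 0.45 | 0.501 | 14% |
| 2 pre, 2 on | 0.5, 1.2 | 0.60 | 0.450 | 26% |
| 1 pre, 2 on | 0.7, 0.9 | 0.60 | 0.509 | 21% |
| 1 pre, 2 on | 0.5, 1.2 | 0.80 | 0.465 | 39% |

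**4. Power with treatment-by-visit and a common pre-drug mean** (two pre-drug visits). Let c = (1 + ρ)/2, which is 0.85 or 0.75. The variance left after adjusting for the pre-drug mean is:
- Visit 3–4 average: 3.24(c − ρ²/c) = 0.886 or 1.350; SE 0.298 or 0.367; power 84% or 89%.
- Visit 4 alone: 3.24(1 − ρ²/c) = 1.372 or 2.160; SE 0.370 or 0.465; power 66% or 71%.

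**5. Is the interaction enough by itself?** Assume 10,000 reads per sample (a depth mentioned under Initial microbiome analysis) and the plan's mean abundance of 10.4%. The expected count is 1,040, which is also the Poisson variance.
- The within-subject SD is 1.8√(1−ρ) = 0.986 or 1.273 points, or 98.6 or 127.3 reads.
- The true variance is larger than Poisson by 1 + 98.6²/1,040 = 10.3 (ρ = 0.7) or 1 + 127.3²/1,040 = 16.6 (ρ = 0.5).
- A nominal 5% Wald test then rejects a true null with probability P(|Z| > 1.96/√10.3) = 54% or P(|Z| > 1.96/√16.6) = 63%.
- In 300 simulated null datasets, the arm-by-Visit-4 test rejected 60% (ρ = 0.7) and 64% (ρ = 0.5). A t-test on log change rejected 5% and 6%.

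**The case against.** **The interaction may be implied.** The text gives no formula and does not exclude the term. Listing treatment and time as fixed effects may only separate them from the random subject effects, and the stated aim presupposes an interaction. This stands in part: a reader might infer that the sponsor has settled on a main-effects model, and the documents do not show that. They show only that the term is not named.

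**The halving depends on coding and visits.** If treatment were coded as zero before the first dose, the additive model would recover the full average effect (simulated log ratio −0.69 against a true −0.69). It would still give no separate test at each visit. The paragraph states neither the coding nor which visits enter. A reader might take two pre-drug visits as certain; the Study Design prose implies one.

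**Other analyses estimate change.** The t-tests of within-subject change point to an outcome list that includes the top 10 genera, and the Microbial bioinformatics section plans pre-to-post and between-arm comparisons. So the drug effect would not be hidden altogether. Neither analysis repairs the model named for RCT sizing.

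**The vegan models.** A reader might infer that they share the defect. With no formula given, that cannot be shown.

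**It is an exploratory pilot.** True, and ACT is the primary outcome. But estimating the response is a stated purpose, so a diluted estimate still matters.

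**Conclusion.** The point holds in a conditional form. As worded, the model gives one rate ratio for all visits and cannot meet its stated aim under either coding. With arm coding and all four scheduled sputum visits, it loses about half the effect (50–58%); with one pre-drug visit, about 33–42%. The power figures rest on compound symmetry, a constant on-drug effect and a linear approximation to the count model.

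It would be tempting to say that adding the interaction restores roughly 80% power whichever contrast is chosen. It does not: Visit 4 alone reaches 66–71%, and only the Visit 3–4 average exceeds 80%. Nor is the interaction safe in a plain Poisson random-intercept model, where the false-positive rate is about 60%.

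This should be fixed before analysis. It does not touch the ACT analysis and loses no data.

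**What to change.** In the Poisson modeling paragraph:
- Specify treatment-by-visit, with visit as a factor and a common pre-drug mean across arms. State how treatment is coded and which visits enter.
- Prespecify whether the Visit 3–4 average or Visit 4 leads, and use that contrast for RCT sizing.
- Add visit-level overdispersion, through an observation-level random effect or a negative binomial model. Carry the same model into the imputation and diversity inference.

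In the Microbial bioinformatics paragraph, state that the treatment-by-visit term is the one tested in the vegan models. Reconcile the visit timing in the Study Design prose with the Schedule of Events and the Study Drug section.

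The cost is a short SAP revision and no new data. The downside is a few more parameters and wider intervals than a plain Poisson model would report; those wider intervals are the honest ones.
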